We plan to conduct this study as a feasibility study. It will be a 3-arm randomized controlled trial where participants will be randomized to one of the three following groups: music listening intervention involving instrumental STM, non-musical sounds involving nature sounds, or standard of care on the GAU (control). The patients will be randomized in equal ratios to the 3 groups using a random number generator. Each intervention will take place over 7 consecutive nights. The music or non-musical sounds will be played throughout the whole night for each patient in those groups.

We note that patients' medical situation will likely change throughout their hospitalization stay and this may be a confounding factor affecting their sleep. We also note that patients may be discharged prior to completing the 7-day intervention.

Selection of music and non-musical sounds:

The music selected in our study will be pleasant instrumental STM in a major mode. It will also be low contrast (without periods of silence). The non-musical sounds will be low-contrast nature sounds such as waves. We plan to use non-musical sounds that align with the frequency range of the musical stimuli.

Study outcomes:

The primary outcome to be measured will be sleep quality. This will be measured objectively by sleep logs and subjectively through patients' own perspectives of their sleep.

Secondary outcomes will include patients' sleep quality assessed by smart watches. We will evaluate if the data from the smart watches correlates to patients' sleep log and to their subjective view of their sleep quality.

Other secondary outcomes will include the patients' mood (depression, anxiety), level of pain, the number medications used for sleep (PRNs and regular medications), and the duration of stay in hospital. Of note, as part of our study, we will not be administering any medications to the patients, and we do not expect there to be any alcohol use on the GAU. We will simply be taking note if the patients received any medications for the indication of facilitating their sleep, prescribed by their treating physician. On the GAU, the patients will be assessed daily their treating physician for their medical management.

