We will also assess how much the participants enjoy listening to the selected music and non-musical sounds in our study throughout the intervention. We will not include the MMSE as part of our outcomes as it is often unreliable when patients are admitted to hospital with an acute illness and may not be at their cognitive baseline.

Other secondary outcomes will include feasibility measures: the number of participations and refusals, the number of eligible patients and exclusions, protocol adherence, the availability of the data, the time

needed to collect the data, the cost, and the standard deviation of the primary outcome measures to help estimate the sample size required to achieve sufficient statistical power in subsequent studies.

Study population:

This study will include patients admitted to the GAU at St. Mary's hospital in Montréal over the six-month study period (March to August 2022). As many of the patients admitted to the GAU have major neurocognitive disorder (MNCD), we will include them in our study (MNCD of any stage, including Alzheimer's disease). Furthermore, we will include patients who take medications for sleep in our study, and they will be randomized into the 3 groups like all the other participants. We will only include patients who accept to participate in the study with consent obtained either for the patient or from their substitute decision maker if they are deemed not capable of providing consent (to participate in this research project) themselves by their treating physician.

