The patients' baseline characteristics will be noted upon entry into the study: admitting diagnosis, demographics (age, sex) and music sophistication. Patients' music sophistication will be evaluated using the General Musical Sophistication Subscale (GMSS) which is embedded within the Goldsmiths Musical Sophistication Index (Gold-MSI) and includes 18 items with excellent internal consistency (appendix 1) [37]. Furthermore, patients' normal sleep hygiene/routine will also be evaluated prior to the intervention specifically to see if they already listen to music or non-musical sounds before/while they sleep. Finally, as we will be including patients who use medications for sleep in our study, we will note what type of medication(s) the participants are taking. Specifically, we will categorize the medications in the following categories: benzodiazepines, antidepressants, antipsychotics, melatonin, or other; and we will note if the indication is specifically for sleep or not.

The following patients will be excluded from our study: patients who already listen to music or nonmusical sounds as part of their sleep routine, those with medical instability which limits their ability to participate in the study (determined by the patient's treating physician), those who have a diagnosis of a sleep disorder including obstructive sleep apnea and REM sleep behaviour disorder, and those who are unable to communicate in English or French. Furthermore, we will exclude patients with behavioural issues that limit their participation in the study; specifically, those that have agitation or hyperactivity that limits their compliance with the intervention as can be seen in cases of severe BPSD or hyperactive delirium. We will discuss with the treating physician to determine if the patient's behavioural issues would limit their ability to participate in the study and thus require exclusion from the study. Finally, we will also exclude patients with severe hearing impairment, specifically those for whom their hearing impairment affects their ability to communicate their consent for this study and to listen to music.

Recruitment and consent:

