Sleep logs will be used to clinically track patients' sleep (bedtime, sleep onset, wake time) (appendix 3). This information will be gathered by the research assistants from the nursing report in the morning after the night shift. The number and duration of naps that patients take during the day will also be tracked. Subjective measures of sleep will be assessed via the Insomnia Severity Index (ISI) questionnaire (appendix 4) which will be administered to the patients daily. The ISI questions will be slightly modified so that the questions focus on patients' latest night of sleep, not on their sleep over the past 2 weeks, as this questionnaire will be administered daily. The ISI has been shown to be a reliable and valid tool as an outcome measure in insomnia treatment and research in older patients [38]. The ISI has been used in previous studies for older patients [39-41].

The patients will wear smart watches (Samsung Galaxy Fit2) at all times throughout the study period. The smart watches assess sleep quality by tracking a set of non-staging sleep parameters including total sleep time, sleep onset latency, wake after sleep onset, and sleep efficiency. Smart watches have shown good inter-test reliability (96-99%) when assessing sleep parameters in individual adults, and although more limited in comparison to laboratory-based polysomnography, smart watches can allow for the examination of changes within individual patients [42]. The data collected from the smart watches will be time stamped and extracted by the study investigator without any identifying information. We will assess if the data from the smart watches correlates to patients' sleep logs and their subjective view of their sleep quality.

The data on patients' mood will be assessed via visual analog mood scales of specifically 8 emotions: afraid, confused, sad, angry, energetic, tired, happy, and tense (appendix 5). These will be administered to the patients daily throughout the study period. Pain will also be assessed via a visual analog scale that the patients will be asked to answer daily (appendix 6). The data on the number of medications used for sleep (PRNs and regular medications) will be gathered at the nursing report in the morning after the night shift. The data on duration of stay in hospital will be gathered via chart review.

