Dissemination plan:

18

We plan to publish a manuscript of our results in a suitable specialized journal. The results with also be presented as oral presentations at Medical Grands Rounds at St. Mary's Hospital and Geriatric Medicine Grand Rounds at the MUHC (McGill University Health Centre). Furthermore, the results will be presented at the AMGQ (Association des médecins gériatres du Québec) conference in May 2023.

Expected impact of findings:

As this is a feasibility study, the goal is to show that it is possible to conduct a larger study with the same objectives and methodology. The ultimate goal is to create high-quality evidence to support (or refute) our hypothesis that music listening interventions are effective at facilitating sleep for patients admitted to the GAU. This would be a safe and cost-effective intervention to improve the health outcomes of this vulnerable population.

Schematic flow of the methodology of the study:

[figure not shown]
Recruitment of patients admitted to the GAU at St-Mary's hospital.

Exclusion criteria:

- Already listen to music or non-musical sounds as part of their sleep routine
- Medical instability
- Behavioural issues
- Diagnosis of sleep disorder
- Hearing impairment

Initial assessment of patients entered into the study:

- Age
- Sex
- Admitting diagnosis
- Music sophistication (modified version of Goldsmiths Musical Sophistication Index)
- Bed location in room (if next to window)

Music Intervention Group

Music listening exercise (instrumental STM) played at bedtime and overnight for 7 consecutive nights.

Non-Musical Sounds Group

Non-musical sound listening exercise (nature sounds) played at bedtime and overnight for 7 consecutive nights.

Control Group

Standard of care on the GAU which involves an adapted in-hospital approach to geriatric patients, for 7 consecutive nights.

Music Intervention Group

Daily administration:

- Insomnia severity index questionnaire (ISI)
- Visual analog mood scale (VAMS)
- Visual analog pain scale
- Questions on music enjoyment

Daily information from nursing report in AM:

- Sleep log of the preceding night
- Number and duration of naps during previous day
- Medications used for sleep
- Adherence to protocol: headphones on or off, and mp3 player turned on or off throughout night

Smart watch worn 24 hours/day, total 7 days

Sound recorder placed at bedside each night

Non-Musical Sounds Group

Daily administration:

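### Cheap improvement: no pre-intervention value of the ISI or the sleep log is scheduled at entry, and the first day of the daily measures is not stated

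*Protocol*

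**What the plan says.** The Study population section states that "baseline characteristics will be noted upon entry into the study: admitting diagnosis, demographics (age, sex) and music sophistication". It adds two sleep-related items. The usual sleep routine "will also be evaluated prior to the intervention specifically to see if they already listen to music" or other sounds. Sleep medication is noted by type in five categories, with whether its indication is sleep.

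The Schematic flow has its own list, headed "Initial assessment of patients entered into the study": age, sex, admitting diagnosis, music sophistication and bed location. The ISI and the item "Sleep log of the preceding night" appear only further down, under each allocated group. The watch is worn for 7 days in total, equal to the 7 intervention nights.

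Under Data collection procedure, the ISI is given daily and reworded to the patient's "latest night of sleep, not on their sleep over the past 2 weeks". The log comes from the morning nursing report. No first day is given for either.

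Study outcomes lists as a feasibility output "the standard deviation of the primary outcome measures to help estimate the sample size required to achieve sufficient statistical power in subsequent studies". Data analysis plans multiple regression without naming covariates.

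**The concern.** A starting value of the outcome is often the most useful covariate in a small trial, and here no step is scheduled to collect one. The rewording of the ISI sharpens this. A two-week recall given early in the study would still have reached back before entry; a latest-night ISI given after night 1 describes only a night on allocated treatment. Which covariates enter the regression can be left to a statistical analysis plan, but no such plan can recover a patient-reported score that was never taken.

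Two things are at stake. One is some precision in the sleep comparison, together with the ability to see whether the arms started with similar sleep. The other is the correlation between baseline and outcome, which would help to size a larger trial that adjusts for baseline.

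**Working it through.** **Is a pre-intervention value scheduled anywhere?** Set side by side, the two entry lists differ in detail: the flow scheme omits the sleep routine and medication, and adds bed location. Neither contains the ISI or the log, and no other section places either measure before night 1. The 7-day watch period shows no run-in night.

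**Planned size.** Sample size gives 2 enrolments per week and Study population gives six months, about 26 weeks: 2 × 26 = 52, consistent with the stated figure of around 50. Equal allocation to three arms gives 50/3, about 17 per arm.

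**Chance imbalance.** With 17 per arm, the baseline difference between two arms has a standard error of √(2/17) = 0.34 SD. A chance gap above 0.5 SD in a given pair has probability 2 × [1 − Φ(0.5/0.343)], about 14%.

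**Precision gain at N = 50.** Let r be the correlation of one pre-intervention night with the mean of the on-study nights. The protocol gives no value, so r is an assumption throughout.
- Cost of one covariate with three arms: 1 + 1/(50 − 3 − 1 − 1) = 1.022.
- Break-even: r = √(1 − 1/1.022) = 0.147.
- Effective N = 50 / [(1 − r²) × 1.022]; the SE ratio is the square root of 50 over effective N.

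| Assumed r | Effective N | SE ratio |
|---|---|---|
| 0.2 | 51.0 | 0.991 |
| 0.3 | 53.8 | 0.964 |
| 0.5 | 65.2 | 0.876 |

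**What r might be.** Two correlation patterns bracket the plausible range.
- Equal correlation ρ between all nights: r = ρ / √[(1 + (k − 1)ρ)/k] for the mean of k nights.
- Decaying correlation, AR(1), with adjacent-night value ρ: r = mean of ρ^d for d = 1 to 7, divided by the square root of the mean of all ρ^|i−j|.

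| ρ | Equal, 7 nights: r | Equal, 3 nights: r | AR(1), 7 nights: r | AR(1): effective N |
|---|---|---|---|---|
| 0.1 | 0.21 | 0.16 | 0.04 | 49.0 |
| 0.2 | 0.36 | 0.29 | 0.08 | 49.2 |
| 0.3 | 0.47 | 0.41 | 0.12 | 49.7 |
| 0.5 | 0.66 | 0.61 | 0.24 | 51.9 |

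Decay is plausible here, since Study design says that the "medical situation will likely change throughout their hospitalization stay". The three-night column is shown because "patients may be discharged prior to completing the 7-day intervention". To reach r = 0.3 over 7 nights, nights must correlate at about 0.16 under equal correlation, or adjacent nights at about 0.58 under AR(1).

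**How well r would be estimated.** For r = 0.5 and n = 50, Fisher's z gives tanh(0.549 ± 1.96/√47), a 95% interval of 0.26 to 0.68.

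**The case against.** The strongest reply is that nothing in the protocol is wrong. The study is a feasibility trial without a power calculation, randomisation keeps the comparison free of systematic bias, and the raw SD is enough to size an unadjusted next trial. All of that stands, and it keeps the severity low.

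The possible benefit may also be nil. Under decaying correlation the effective size is 49 to 52 from 50, and even r = 0.5 would be estimated with a wide interval. That stands too; what remains is the descriptive value of knowing how each arm slept at the start.

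A baseline might already be intended. Both measures look back one night, so a first administration on the entry day before night 1 would supply it, and the contents of the log and ISI appendices are not shown. The flow list is plainly not exhaustive, so omission from it alone proves little. A reader might infer that a baseline is ruled out; the documents support only that none is scheduled. They also do not show that the log value must be lost, since it comes from nursing reports that may be retained.

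A reader might further infer that no baseline-adjusted comparison is planned. That is not supported either: the regression covariates are unnamed and may be set in an analysis plan that is not at hand, and sleep medication is already an available sleep-related covariate.

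**Conclusion.** The point holds as a cheap improvement of low severity. The entry assessment schedules no pre-intervention value of either primary sleep measure, and the start of daily collection is left open. For the ISI, a missed value cannot be recovered afterwards.

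The size rests on an r that the protocol does not supply. It runs from no gain below about r = 0.15 to an SE about 12% lower at r = 0.5. These figures assume one covariate, N = 50, complete data and comparison with an unadjusted contrast. Adjustment for sleep medication could already take up part of the gain. The documents do not support reading this as bias, or as a failure of the study's stated aim of supplying an SD.

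**What to change.** After consent, before night 1 and before the allocation is disclosed, give the latest-night ISI once and take the previous night's bedtime, sleep onset and wake time from the nursing report where available. Add both to the entry lists in Study population and in the Schematic flow. If the first daily ISI and log are already meant to fall on the morning before night 1, one sentence in Data collection procedure saying so is enough.

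Use each baseline value as a covariate for its own measure in the regression already planned. Report the baseline-outcome correlation with its confidence interval, and the adjusted SD beside the raw SD.

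The cost is one short questionnaire and one nursing-report entry per patient, using instruments and staff already in place: a few minutes of patient and research-assistant time. Each covariate takes one degree of freedom, about 2% of precision at N = 50. Prior-night log data may be incomplete, for example if sleep onset was not charted before the patient entered the study, and r will be imprecise. Collecting the ISI before disclosure also requires the protocol to state the order of consent, baseline and allocation.

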We predict that a musical listening exercise will more effectively contribute to the facilitation of sleep compared to non-musical sounds and compared to standard of care on the GAU. We plan to conduct this study as a feasibility study. It will be a 3-arm randomized controlled trial where participants will be randomized to either: (1) music listening intervention, (2) non-musical sounds involving nature sounds, or (3) standard of care on the GAU. The intervention will take place over 7 consecutive nights.

The primary outcome will be sleep quality, which will be measured objectively using sleep logs and subjectively through patients' own perspectives of their sleep through the Insomnia Severity Index. Secondary outcomes will include patients' sleep quality assessed by smart watches, which we will evaluate to see if the data correlates to the sleep logs and patients' subjective view of their sleep. Other secondary outcomes will include patients' mood, level of pain, number medications used for sleep, duration of stay in hospital, patients' level of enjoyment of the music or non-musical sounds, and feasibility measures.

As this is a feasibility study, the goal is to show that it is possible to conduct a larger study with the same objectives and methodology. The ultimate goal is to create high-quality evidence to support (or refute) our hypothesis that music listening interventions are effective at facilitating sleep for patients admitted to the GAU. This would be a safe and cost-effective intervention to improve the health outcomes of this vulnerable population.

Background/literature review:

Impact of sleep disturbance in older adults

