attention and working memory [12]. Interestingly, global cognitive decline was found in individuals with insufficient (≤ 4 hours per night) or excessive (≥ 10 hours per night) sleep duration in a pooled cohort study from 2020 [13]. Sleep disturbance also leads to increased falls [14], poor quality of life, emotional distress, and decline in physical function [15] which geriatric patients are already at risk for. The profound implications of sleep disruptions on the health and wellbeing of geriatric patients therefore warrants further research that aims to identify methods for improving sleep and quality of life.

Intervention for sleep disturbances

There is a keen focus on the use of non-pharmacological interventions for the facilitation of sleep in these vulnerable patients because of the high risk of side effects related to pharmacotherapy. Benzodiazepines are one of the most widely prescribed classes of medications for insomnia [16]. Their safety and efficacy are significantly restricted by the risk of development of tolerance and dependency with their long-term use [16]. They are also associated with long-term side effects and increased morbidity and mortality [16]. Long-acting benzodiazepines used long-term (>1 month) are listed as medications that should not be used in elderly patients according to geriatric clinical algorithms (e.g., STOPP/START criteria) due to their risk of prolonged sedation, confusion, impaired balance, and falls [17]. Furthermore, other agents, such as antihistamines, tricyclic antidepressants, antipsychotics, and anticholinergics for insomnia should also be avoided in elderly patients owing to their side effect profile [11, 18]. Finally, sedative medications are also used in patients with hyperactive delirium and behavioural symptoms of dementia which are both exacerbated by sleep disturbance. Therefore, if sleep can be improved by non-pharmacological interventions in these cases as well.

Use of music in the older adults

Music interventions are safe and cost-effective non-pharmacological tools for which there is a growing body of evidence for their potential health benefits in multiple domains. Studies with participatory musical interventions showed that there were multiple health benefits in geriatric patients. In a randomized

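### Does excluding diagnosed sleep disorders wrongly shut out patients with charted insomnia, given that users of sleep medication are admitted and the ISI is a primary measure?

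*Protocol*

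**What the plan says.** In Study population, the Protocol excludes "those who have a diagnosis of a sleep disorder including obstructive sleep apnea and REM sleep behaviour disorder". The exclusion list in the schematic flow shortens this to "Diagnosis of sleep disorder", with no examples. Neither place mentions insomnia.

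The same section states that "we will include patients who take medications for sleep in our study" and that these patients are randomised like the rest. At baseline the class of drug is recorded, with benzodiazepines first in the list, and "we will note if the indication is specifically for sleep or not". The Background (Intervention for sleep disturbances) remarks that "Benzodiazepines are one of the most widely prescribed classes of medications for insomnia".

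The Abstract measures the subjective part of the primary outcome by patients' "own perspectives of their sleep through the Insomnia Severity Index". Data collection procedure repeats the choice ("Subjective measures of sleep will be assessed via the Insomnia Severity Index (ISI) questionnaire") and rewords the items so that they ask about the most recent night.

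Under Recruitment and consent, treating physicians screen first with a triage questionnaire that holds the criteria, and a research assistant then confirms eligibility. The questionnaire is Appendix 2; its content is not in the text at hand. Among the feasibility outcomes are "the number of eligible patients and exclusions" and the standard deviation of the primary measures, which is to help size a later trial.

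**The concern.** Insomnia is ordinarily counted as a sleep disorder, and nothing in the criterion exempts it. The Protocol links one of the drug classes it expects to see with insomnia, so a patient taking a benzodiazepine for charted insomnia seems to be let in by one sentence and kept out by another. It also looks odd to measure insomnia severity in a sample from which diagnosed insomnia has been removed.

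If physicians read the criterion differently, one might refer a patient whom another would exclude. The counts of eligible and excluded patients are feasibility results in their own right, and the standard deviation is carried forward. Both would then depend on a reading that the text does not fix. A strict reading might also cost recruits in a trial whose expected enrolment is only just above its aim.

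**Working it through.** **1. The two eligibility rules side by side.**

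- Rule A (Study population, inclusion): use of sleep medication does not prevent entry.
- Rule B (Study population, exclusion): a diagnosed sleep disorder does prevent entry.

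The rules would contradict each other only if A guaranteed entry. It does not; it removes one possible bar, and the exclusions still apply. The section treats cognition in the same way: major neurocognitive disorder of any stage is admitted, yet patients with severe behavioural symptoms that limit participation are excluded.

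The rules can also be applied together, because a patient can receive a drug for sleep without a charted sleep-disorder diagnosis. The Protocol expects mixed use: as-needed and regular drugs, several classes, and indications other than sleep. The benzodiazepine sentence is general background and says nothing about who will be enrolled. What remains is one subgroup, patients with charted insomnia, whose status the text leaves open.

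**2. The ISI.** Entry requires neither an insomnia diagnosis nor a minimum ISI score. The Purpose section targets the sleep of patients admitted to the geriatric assessment unit, and the Background stresses sleep lost because of hospitalisation. In its latest-night form the ISI scores current symptoms, so it can be used in undiagnosed poor sleepers, who stay eligible on either reading. At most, excluding diagnosed insomnia would narrow the range of scores.

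**3. Comparison between arms.** The criterion is applied before randomisation, so either reading, or a mixture of the two, affects all three arms alike. It changes who is studied and does not bias the comparison.

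**4. Recruitment.** Inputs: 2 patients per week and an aim of around 50 (Sample size); March to August 2022 (Study population).

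- The plan's figure: 26 weeks × 2 = 52, consistent with around 50.
- By calendar: 31 + 30 + 31 + 30 + 31 + 31 = 184 days; 184 / 7 = 26.29 weeks; × 2 = 52.6.
- If the last patient must finish 7 nights by the end of August: 177 / 7 = 25.29 weeks; × 2 = 50.6.
- Margin over 50: 2.57 / 52.57 = 4.9%, or 0.57 / 50.57 = 1.1%.

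The Protocol gives no share f of patients with charted insomnia. Its figure approaching 50% is for insomnia symptoms in adults aged 65 and older, not for diagnoses. Suppose the 2 per week counted these patients as eligible and they were then excluded. Enrolment would be 52.57 × (1 − f):

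| Assumed f | Enrolled | Per arm |
|---|---|---|
| 5% | 49.9 | 16.6 |
| 10% | 47.3 | 15.8 |
| 20% | 42.1 | 14.0 |
| 30% | 36.8 | 12.3 |
| 50% | 26.3 | 8.8 |

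These shares are assumptions. Sample size states the rate as patients enrolled, which most naturally means after exclusions; on that reading there is no loss. The aim is approximate and no power calculation was made, so nothing in the plan turns on 50 as a threshold.

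**5. Standard deviation.** Under either reading it describes the population that reading admits. The later trial is planned with the same aims and methods, so if the criterion is carried over and applied in the same way, the estimate fits its use.

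**The case for a change.** The best case for a change is that eligibility belongs in the Protocol and cannot be left to a statistical analysis plan. The other judgement-based exclusions are qualified: medical instability by the treating physician's decision, behaviour and hearing by a description of who is meant. The sleep-disorder criterion has no such limit. Because physicians screen first, the research assistant confirms eligibility only for patients who were passed on, so too strict a reading at the first step would not be caught. The count of exclusions is an outcome, and the wording may be inherited by the larger trial. Amending it would cost little.

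Much of this stands. The wording is open, and the count of exclusions could be somewhat blurred. But inconsistent screening is a possibility, not something the documents show, and the questionnaire that physicians will use may name the disorders. Writing in an exemption for insomnia would also go beyond clarification: it would choose the population for the investigators. Leaving out diagnosed insomnia in order to study sleep disturbed by hospitalisation is a legitimate design; admitting it gives a broader, more mixed sample. Reasonable investigators could prefer either.

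**Conclusion.** The concern does not hold as a fault in the plan. The criterion does not say whether charted insomnia is covered, and that is a real gap in wording. It is one that the study team can settle in screening and report with the exclusion counts. It does not contradict the admission of patients on sleep medication, and it does not conflict with the ISI.

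The effect on bias between arms is nil under either reading. The effect on enrolment cannot be derived: it is zero if the 2 per week is already net of exclusions, and otherwise depends on a share the Protocol does not give. The possible effect on the feasibility counts is confined to patients with charted insomnia. This conclusion assumes that the questionnaire, which could not be seen, does not itself contradict the Protocol text, and that whichever reading is used is carried into the later trial. No wrong result follows from the plan as written, so no change is called for.
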